11. APPENDICES						

## 1. EXECUTIVE SUMMARY.

#### 1.1 Study Title

Randomized controlled study of the efficacy of Elitone Device for the treatment of mild-moderate urinary incontinence in women.

#### 1.2 Objectives

The primary objective of this study is to demonstrate the safety and efficacy of the Elitone device as a conservative treatment for stress urinary incontinence.

### 1.3 Design and Outcomes

This is a randomized controlled study in which subjects are assigned to either a treatment group or a control (sham) group. Pre- and post-study outcome measures evaluate the change in incontinence episodes on women with mild-moderate stress urinary incontinence.

### 1.4 Interventions and Duration

Study participants in the treatment group will receive surface electrical stimulation intended to treat incontinence. Participants in the control group will receive non-therapeutic surface electrical stimulation. Treatment is self-administered in an at-home environment according to a defined schedule. Outcomes are assessed after 12 weeks.

#### **1.5** Sample Size and Population

The population includes women ages 21-75 with mild-moderate stress urinary incontinence. The active and control groups will be enrolled in a 2:1 ratio, totaling 40 and 20 subjects respectively.

## 2. OBJECTIVES AND HYPOTHESES

#### 2.1 Primary Objective

The primary objective of this study is to demonstrate the safety and efficacy of the Elitone device as a conservative treatment for stress urinary incontinence.

#### 2.2 Primary Endpoint

Treatment efficacy is assessed by comparing the average number of stress urinary incontinence episodes per day at the end of treatment to the corresponding pre-treatment number.

Safety is determined by review of Adverse Events as defined in 7.3, and determination of no serious adverse event during the study.

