### 5.3 Description of Evaluations

This research utilizes validated methods for evaluating the clinical impact of the device/treatment, including several identified in the FDA guidance document regarding clinical studies that investigate urinary incontinence. Stress urinary incontinence episodes per day data, obtained from the subject's Daily Log, serves as the primary efficacy outcome measure (see 2.2). Analysis of adverse events serves as the primary safety outcome measure (see 2.2). Evaluations utilized throughout the study are described below. See 9.5 for detail regarding strategies for analyzing the data obtained in these evaluations.

- I-QoL Questionnaire (Pre- and Post-study) the Incontinence Quality of Life (I-QoL) questionnaire is validated tool for assessing changes in the degree to which urinary incontinence affects a woman's quality of life (TR-1131-FORM-2). It comprises 22 questions, to which the subject provides a numeric response on a 1-5 scale. The score is the sum of the numeric responses, which can range from 22 to 110. A change of 2.5 points is considered clinically significant. The I-QoL questionnaire is provided to the subjects as part of pre- and post-study materials. Completed questionnaires are returned to Elidah via mail or electronically (see 10.4).
- 24-Hour Pad Weight Test (Pre- and Post-study) This test is used to quantify the volume of urine leakage. The subject wears an absorbent pad(s) over a period of 24 hours, after which the pad(s) are weighed to determine the mass of any leaked urine. A reduction of ≥50% compared to a baseline measure is considered clinically significant. A mass of less than 1.3g is considered to be "dry", i.e. no leakage. Pre-weighed pads will be sent to the subjects as part of the study materials. During pre- and post-study assessments the subjects will wear the pad(s) for 24 hours, seal the pad(s) in a moisture proof bag, and mail to Elidah for weighing. Note that although this assessment does provide an objective

measure of change in leakage volume, the method is known to be subject to variability, may not be meaningful to patients, and requires subject compliance. For this reason, Elidah has identified this tool as a secondary outcome measure and does not intend to use the data as a primary means for establishing device efficacy.

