### 7.3 Adverse Events and Serious Adverse Events

Adverse events are the primary means for assessing device/treatment safety. Adverse events may be identified through direct communication with the subjects and through analysis of study materials.

For all adverse events, sufficient information will be pursued and/or obtained so as to permit (1) an adequate determination of the outcome of the events (i.e., whether the effect should be classified as a serious adverse effect) and (2) an assessment of the casual relationship between the adverse event and the device/treatment.

Adverse events determined to be associated with the device/treatment will be followed until they are resolved or stabilized. The CTCAE definitions and scoring of Adverse Events will be used.

An **adverse event (AE)** is generally defined as any unfavorable and unintended symptom or finding which either occurs during the study, having been absent at baseline, or, if present at baseline, appears to worsen during the study. Adverse events are recorded regardless of their relationship to the study intervention.

A **serious adverse event (SAE)** is generally defined as any adverse event that results in death, is life threatening, requires inpatient hospitalization or prolongation of existing hospitalization, results in persistent or significant disability/incapacity, or is a congenital anomaly: Grades 3-5.

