## 7.4 Reporting Procedures

Subjects are instructed to report adverse events at the time of occurrence via either phone or email. Adverse events may also be identified during routine communication with the subject (e.g. 6th week follow-up) or review of the subject's Daily Log.

The Data Safety and Monitoring Board will use the following 0 to 5 scale to grade adverse events (AE): 0 = none or event is not clinically significant, 1 = mild AE that does not require treatment, 2 = moderate AE that does require treatment, but resolves completely, 3 = severe AE (e.g. one that results in temporary inability to conduct one or more everyday activities and requires ongoing medical attention), 4 = life threatening or results in permanent inability to conduct one or more everyday activities, and 5 = death.

In the event of an AE rated ≥2 the Clinical Director will instruct the subject to obtain medical treatment from a qualified healthcare professional. If the subject becomes ill or is physically injured due to the use of the Elitone™ device, she will not be responsible for the costs required to diagnose or treat such injury. The costs of diagnosis and medical care for any complication, injury, or illness caused by the study device or properly performed non-standard of care investigational procedure required by the study will be covered by Elidah, as long as the subject has followed the study protocol. The subject will not lose any of her legal rights and she does not release Elidah and the study staff from liability for mistakes or intentional misconduct by participating in the study.

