## 9.4 Interim Analyses and Stopping Rules

The study will include an interim analyses after 30 and 45 subjects have completed enrollment. The Hyabittle-Peto method will be used determine whether the study should be stopped due to extreme differences between the active and control groups. At either interim analysis if the p-value for the primary efficacy outcome is <0.0013 the study will be determined to have met the endpoint.

In the event of a serious adverse event related to the device/treatment the study will be halted until the safety issue can be addressed (see 7). Due to the small enrollment size, a pre-specified number of adverse events will not be used to trigger an interim analysis or early end to the study.

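### As worded, the primary safety criterion does not exclude unrelated or sham-arm serious adverse events, and zero events in 40 active subjects would not by itself demonstrate safety

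*Combined protocol and SAP*

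**What the plan says.** Section 2.2 of the combined protocol and SAP, headed Primary Endpoint, has an efficacy paragraph and a safety paragraph. The safety paragraph reads: "Safety is determined by review of Adverse Events as defined in 7.3, and determination of no serious adverse event during the study". Section 5.3 confirms that adverse event analysis is the primary safety outcome measure and refers back to 2.2.

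Section 7.3, which 2.2 cites, contains three relevant statements:

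- On capture: "Adverse events are recorded regardless of their relationship to the study intervention".
- On assessment, for all adverse events, it seeks enough information for "an assessment of the casual relationship between the adverse event and the device/treatment" (the plan prints casual, evidently for causal).
- On seriousness, it lists the usual outcomes and closes with "results in persistent or significant disability/incapacity, or is a congenital anomaly: Grades 3-5". The definition has no relatedness element.

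Section 9.4 does use a relatedness qualifier, for a different purpose: "In the event of a serious adverse event related to the device/treatment the study will be halted until the safety issue can be addressed".

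Section 9.5 sets out the primary efficacy analysis, three formal secondary tests and some further analyses. It has no safety population, arm comparison, confidence limit or acceptable rate for serious events. The sample size in 9.1 rests on responder rates alone.

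**The concern.** Sections 1.2 and 2.1 set out to demonstrate safety as well as efficacy, and 9.6 says the study is meant partly to support FDA clearance. The safety criterion therefore has to be readable in only one way before the data are seen.

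At present it is not. An unrelated hospital admission in a sham subject would not trigger the halt in 9.4, yet on the words of 2.2 it would mean that the no-serious-event condition was not met. Whether it counts would have to be settled after the event. Under 10.5, adverse events are reviewed by a board that includes the sponsor's Clinical Director and a person responsible for the device technology.

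The opposite outcome is also a problem. If no serious event occurs, 2.2 invites the statement that safety was shown, with nothing in 9.5 to say how large a risk the data leave open.

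**Working it through.** **Figures in the plan.** There is no safety figure to reproduce. The treatment-arm sizes in 9.1 (31, 16 and 12) can be recovered with an unpooled two-proportion normal approximation at one-sided 0.025, 80% power and 2:1 allocation (30.5, 15.1 and 11.5 before rounding up). They concern efficacy only and have no bearing here.

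**Inputs**

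- Subjects: 40 active and 20 sham (1.5), 60 in all; 70-80 likely to be enrolled (5.2, 9.1).
- Observation time: 12 weeks, with a thirteenth as needed (Table 5-1).
- Background rate of unrelated serious events: not given. Section 3.2 says earlier sponsor studies saw none, without a denominator. I assume 1% and 2% per person-year.

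**Chance of at least one unrelated serious event, whichever arm it falls in.** With n subjects, t years each and rate r, P = 1 - exp(-n × t × r), where t is 12/52 = 0.231 or 13/52 = 0.25.

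- n = 60, r = 1%: 1 - exp(-60 × 0.231 × 0.01) = 12.9%; at 13 weeks, 1 - exp(-0.15) = 13.9%.
- n = 60, r = 2%: 24.2% at 12 weeks; 1 - exp(-0.30) = 25.9% at 13 weeks.
- n = 80: 16.9% to 18.1% at r = 1%; 30.9% to 33.0% at r = 2%.
- The 20 sham subjects alone: 4.5% to 4.9% at r = 1%; 8.8% to 9.5% at r = 2%.

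If only related events counted, and relatedness were judged correctly, a device that causes none would never miss the criterion.

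**What zero events would show.** The exact upper limit for 0 of n is 1 - 0.05^(1/n) (one-sided 95%) or 1 - 0.025^(1/n) (two-sided 95%).

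- 0 of 40 active: 1 - 0.05^(1/40) = 7.2%; 1 - 0.025^(1/40) = 8.8%.
- 0 of 53 active (about two thirds of 80): 5.5% and 6.7%.

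Put the other way, a true related risk of 2% in 40 active subjects gives no related event in 0.98^40 = 45% of trials. At 5% it is 0.95^40 = 13%. These results need no background rate.

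**Grade wording.** Section 7.3 ties serious events to Grades 3-5 and names CTCAE scoring. Section 7.4 gives its own 0 to 5 scale, on which grade 3 is, for example, a temporary loss of an everyday activity with continuing medical attention. That could bring in events meeting none of the listed seriousness outcomes, which would raise the chance figures above. The two sections need to be reconciled.

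**The case against.** The strongest reply is that 2.2 defines safety through the review of adverse events in 7.3, and 7.3 requires a causality assessment for every event. On that view relatedness is already part of the criterion, and the sentence about recording events regardless of relationship governs data capture only. This is a fair reading and may be what was meant. It does not close the gap: no sentence says how the review and the no-serious-event clause combine, or that the review can set an event aside.

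Four further points limit how far the concern can be taken.

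- A reader might infer that one serious event fails the study. The documents do not say so. The hypotheses in 2.3 concern efficacy, the interim success rule in 9.4 uses the efficacy p-value, and 10.6 points to 9.5 for study success, where there is no safety test.
- A reader might infer that 2.2 and 9.4 contradict each other. An endpoint can properly be broader than a halting trigger. The difference shows only that the qualifier was available and was not carried into 2.2.
- A reader might assume background rates of 5-10% per person-year, which would give about 50-78% for 60 subjects. Nothing in the documents supports those rates, and 4.2 excludes cancer, heart problems, epilepsy, neurological disorder, pregnancy and severe obesity.
- Counting related events in the active arm only would be a mistake. Under 6.6 and 9.3 the sham also delivers perceptible current, so a device-related event can occur in a sham user.

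An all-cause count also has the merit of not depending on judgement. That stands, and it is why the all-cause table belongs in the report.

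**Conclusion.** The concern holds as a defect in a stated criterion. Section 2.2 leaves open whether unrelated and sham-arm serious events count, and 9.5 supplies no analysis to settle it. The size of the chance miss, about 13-26% for 60 subjects, rests on the assumed 1-2% per person-year and on the literal reading. It would be higher with 70-80 treated subjects or a higher rate, and lower with a lower one. The limits of 7.2% and 8.8% follow from 40 active subjects alone. The finding is about the meaning of the safety result in either direction; it does not show that chance decides whether the trial succeeds. The change should be made before any data are unblinded.

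**What to change.** - **Section 2.2.** Reconcile it with 7.3 and 9.4 by stating the safety endpoint as device- or treatment-related serious adverse events, with relatedness assessed blind to arm. The blinding needs to be written in, because 6.6 has the same board review control subjects who report pelvic floor contraction, so it will learn some assignments. This concerns the endpoint only; no change to the halt rule is proposed.
- **Section 9.5.** Add a safety analysis of related and all-cause serious adverse events by arm, including any device-related event in sham users, among all subjects who received a device, with exact 95% confidence limits. State the safety conclusion as the upper limit, not as the absence of events.
- **Scope.** Say whether serious events during the optional active treatment of control subjects (4.4) are counted or reported separately, and align the seriousness and grading wording of 7.3 and 7.4.

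No new visits, subjects or data items are needed. The cost is a slightly less favourable safety statement, since an upper limit replaces a bare zero, and a related-event count that depends on judgement. The all-cause table by arm offsets the second.

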### 2.3 Hypothesis

The null hypothesis reads: The number of subjects treated with Elitone who achieve a clinically meaningful reduction ( $\geq$ 50%) in stress urinary incontinence episodes per day against baseline is not different than the control group.

The alternative hypothesis is that: The number of subjects treated with Elitone who achieve a clinically meaningful reduction ( $\geq$ 50%) in urinary stress incontinence episodes per day against baseline is statistically significantly greater than the number who do so in the control group.

## 2.4 Secondary Objectives

The secondary objectives are to characterize the device's efficacy at improving continence based on other meaningful clinical endpoints. This data may be useful to support future product marketing claims including support for over-the-counter use and mixed/urge incontinence. Further, certain information may inform opportunities for future product improvements.

## 2.5 Secondary Endpoints:

Endpoints that support the secondary objectives are listed below. Further description is provided in 5.3 and 9.5.

- 24h Pad Weight Test
- Incontinence Quality of Life score (I-QoL)
- Pads per Day
- Urge Incontinence Episodes or Bathroom Visits per Day
- Usability Data (e.g. Ease of Use, Satisfaction, Preferred Intensity Settings)

### 3. BACKGROUND AND STUDY RATIONALE

#### 3.1 Background on Condition, Disease, or Other Primary Study Focus

Urinary incontinence (UI) is a widely prevalent condition affecting approximately 1 in 3 women over the age of 30, and 1 in 2 women over the age of 50. Although a very private concern, it has far-reaching physical, psychological, social, and economic implications. For example: UI has been found to reduce health-related quality of life measures, with a strong correlation with depression, UI is the number one reason for entry into nursing homes, and the annual cost to Medicare has been estimated at \$10 billion, and at \$20 billion for the entirety of the US healthcare system. 75% of these women are specifically affected with Stress Urinary Incontinence (SUI), which is the loss of continence due to weakened pelvic floor muscles, resulting from a variety of factors including child-bearing, athletic pursuits, trauma, and aging. Their urine leakage occurs when physical exertion (e.g. sneezing, lifting, running) increases intra-abdominal pressure. There are no medications that address SUI, and while surgery can provide relief, it is painful, expensive, and requires hospitalization and multiple weeks of recovery. Additionally, often women do not want the medication that is available for Urge Urinary Incontinence (UUI) due to potential interference with other medications.

Non-surgical strengthening of the pelvic floor muscles has proven effective in treating most SUI and is first-line treatment for UUI, and this is typically achieved through Kegel exercises, biofeedback, weighted cones or intravaginal electrical muscle stimulation (EMS). However, subjects routinely struggle to perform Kegel exercises correctly or with sufficient frequency (3x/day for 3-6 months) which leads to low compliance. Introducing intravaginal devices or an intravaginal probe necessitates a private location and dedicated treatment time (often at a treatment center), further challenging the likelihood of adoption.

To complicate matters, 4 out of 5 sufferers do not speak with their primary care physician until symptoms have intensified and persisted for numerous years (6.5 years on average), and others do not consult a specialist (i.e. urologist) because they fear the recommendation of surgery. This leads to two thirds of affected women suffering quietly without treatment while conditions worsen. Thus, the need exists for a non-surgical means of strengthening the pelvic floor muscles that has a higher rate of patient adoption and compliance than current solutions.

### 3.2 Study Rationale

There is a long history of use of intravaginal EMS for treatment of SUI, and it is predicated on the assumption that proximity of the electrodes to the pelvic floor muscles is of primary importance. This is largely accurate. However, appreciating that subjects who seek help most often ultimately fail treatment due to adoption and compliance issues, it is equally important to consider whether the psychological or physiological barriers associated with intravaginal EMS offset any benefit from the treatment's intimate electrode placement.

Several recent clinical reports suggest that a pattern of surface electrodes placed in the suprapubic and ischial tuberosity regions are as effective as intravaginal electrodes at retraining the pelvic floor muscles. In these studies, treatment was administered by a clinician who placed four separate electrodes on the defined tissue region and delivered prescribed pulse waves during regular training sessions. Unfortunately, the need to deliver this treatment in a clinical environment makes it burdensome to the patient and the health system.

Building on these findings, Elidah has developed a wearable, SUI specific EMS device configured for application by the patient and for use outside the clinic, allowing treatment at home and potentially accelerating the rate and efficacy of muscle retraining.

Surface electrodes have been used for EMS and transcutaneous electrical nerve stimulation (TENS) applications since the 1970's. They have an established history of safe and efficacious across a range of anatomic application sites, and the FDA considers electrodes to be low risk devices: "*Electrodes are a Non-significant risk device, no IDE needed*" (*Non-implantable Electrical Incontinence Device*).

Elidah has conducted clinical trials of similar design (WIRB 20162650), and using the same or similar devices (WIRB 20180640), and observed clinically meaningful improvements in incontinence symptoms without serious adverse events. The current protocol is intended to expand on that earlier work through controlled study that closely replicates real-world use of the device.

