## 4.2 Exclusion Criteria

Subjects will be excluded from enrollment if they meet any of the following criteria:

- Severe incontinence as determined by self-reported >5 accidents in 24-hr period
- Currently pregnant, may be pregnant, attempting to become pregnant, or delivery within previous 6 weeks
- Implanted cardiac device, untreated cardiac arrhythmia or suffer from other heart problems.
- Cancer, epilepsy or cognitive dysfunction
- Vaginal or pelvic surgery within previous 6 months
- Complete denervation of the pelvic floor
- History or symptoms of urinary retention, extra-urethral incontinence, overflow incontinence
- Active urinary tract infection (UTI) or history of recurrent UTIs (more than three in a year)
- Recurrent vaginitis (bacterial/fungal)
- Pelvic pain/painful bladder syndrome
- Underlying neurologic/neuromuscular disorder
- Severe Obesity as defined by BMI >= 35
- Chronic coughing
- Impaired decision making, drug or alcohol dependence, or suicidal thoughts.
- Anyone who lacks the capacity to consent for themselves or who requires a legal representative to give informed consent.

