## 6.6 Control/Sham Device

Subjects in the control group will receive a sham device that is identical to the Elitone device except for the firmware parameters that define the stimulation waveform and therapy session.

The stimulation waveform for the sham occurs as a higher frequency and lower current, and the treatment session duration is also reduced. These parameters and intended to elicit a surface sensation, but not to induce contraction of the pelvic floor muscles or to have a therapeutic benefit.

As part of the post-study surveys subjects will be asked to describe any sensation they felt, whether they felt any contraction of the pelvic floor, and whether they believe they received a treatment or a sham device. The Data Safety and Monitoring Board will review the Case Repot Forms of any subjects in the control group who report contraction of the pelvic floor muscles (see 10.5)

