## 9. STATISTICAL CONSIDERATIONS

#### 9.1 Sample Size and Power Analysis

The study is designed to test the null hypothesis that the treatment group and control group are not different (see 2.3). Specific reference is made to the number of subjects who achieve a  $\geq$ 50% reduction in stress urinary incontinence episodes per day when comparing the final outcome to a baseline measure. Several comparable studies were identified in the literature in which similar " $\geq$ 50% reduction in episodes" metrics were reported. From these, sample-size calculations were performed to provide confidence that sufficient subjects would be enrolled to protect against Type II error. Each of these calculations target 80% power and assume an alpha of 2.5%, a 2:1 treatment to control randomization ratio, and a single-tailed test.

• From Sand *et al*, 48% of subjects in the active group (2 treatments per day) were responders compared to 13% of subjects in a control (sham) group. Using these values in a chi-squared sample size calculation one finds that the treatment group for the proposed study needs to enroll 31 subjects.

<sup>1 Sand et al, "Pelvic floor electrical stimulation in the treatment of genuine stress incontinence: A multi-center, placebocontrolled trial", Am J Obstet Cycecol, 173(1):72-79, July 1995.

- From Richardson *et al*, 62% and 73% of subjects (1 treatment/day and 1 treatment every other day) were responders. This study makes reference to the response rate for the sham group in the Sand et al study (13%). Using the 62% and 13% values in a chi-squared sample size calculation one finds that the treatment group for the proposed study should include 16 subjects.
- From a similar, ongoing study in which Elidah is also the Investigator (WIRB-20162650), to date, 71% of subjects are responders. Conservatively estimating the control responder rate at 15% (about the average rate reported in the AHRQ meta-analysis for the control groups in studies using vaginal EMS, Table F97), using a chi-squared sample size calculation one finds that the treatment group for the proposed study needs to enroll 12 subjects.

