#### 9.3 Blinding

Subjects will be blinded to their treatment group. As described in 6.6, with the exception of the firmware loaded on the Controller component, the devices used in the active and control groups are identical, so visualization and handling of the device by the subject will not compromise the blinding. The devices in both groups generate an electrical output that is perceived by the subject, which reduces the risk of subjects identifying themselves as in the control group. The device user manual (TR-1131-FORM-12) and subject instructions (TR-1131-FORM-15) have been modified/written to eliminate language that might suggest to a subject that she is one group or the other. Similarly, study personnel will be instructed to avoid use of language that might indicate which group a subject is enrolled.

Randomization as defined in 9.2 is implemented by an individual who does not interact with the subjects. Study staff who interact with the subjects are blinded to the randomization. Note however, that there is a risk that study staff who interact with the subjects may be informed of group assignment based on comments by the subjects during the study (e.g. if the subject

<sup>2 Richardson et al, "Pelvic floor electrical stimulation: A comparison of daily and every-other-day therapy for genuine stress incontinence", Adult Urology, 48(1):110-118, 1996.

describes the stimulation in a way that makes the stimulation identifiable). Such comments would be documented in the subject's Case Report File. This unblinding would have little impact on data integrity as the study personnel is not involved in the reporting of outcome measures.

Study personnel who analyze individual subject data will be blinded to group assignment. For example, baseline and 12th week episodes/day calculations and pad weight measurements will be made for each subject by blinded study personnel. Later, when group analysis is performed, blinding will be necessarily broken due to the unequal enrollment ratio.

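### Women who are or were in another Elitone study are not excluded; they may recognise the sham, and the blinding argument in 9.3 does not cover them

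*Combined protocol and SAP*

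**What the plan says.** **Earlier studies.** Section 3.2 reports that "Elidah has conducted clinical trials of similar design (WIRB 20162650), and using the same or similar devices (WIRB 20180640"). Section 9.1 uses one of them for planning: "From a similar, ongoing study in which Elidah is also the Investigator (WIRB-20162650), to date, 71% of subjects are responders". Section 6.1 treats both as earlier work and says that software, waveform and regimen have changed only slightly since.

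**Eligibility.** Section 4.2 opens with "Subjects will be excluded from enrollment if they meet any of the following criteria" and lists 15 criteria. None concerns participation in another study of this sponsor, use of the Elitone device, or use of any pelvic-floor stimulator. Section 4.1 is silent on this too. Section 11.2 adds only minors, women who do not speak and read English, and women who cannot consent. The duplicate check in 4.3 looks for repeat entries to this trial's own survey.

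**Sham.** Section 6.6: "The stimulation waveform for the sham occurs as a higher frequency and lower current, and the treatment session duration is also reduced". It is meant to be felt at the surface without contracting the pelvic floor. The active session lasts 20 minutes (6.2).

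**Blinding.** Section 9.3 relies on devices that look identical, on neutral manuals and instructions, and on a perceptible output in both arms, "which reduces the risk of subjects identifying themselves as in the control group". Section 6.6 asks each woman afterwards what she felt, whether she felt a contraction, and which device she thinks she had. Section 9.5 plans no analysis of those answers and none by prior use.

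**Primary outcome.** Responder status is computed from the Daily Log that the woman keeps herself (5.3, 9.5).

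**The concern.** A sham protects a self-reported outcome only as long as the woman cannot tell which device she has. Identical housings and a perceptible output serve that purpose for someone with nothing to compare against. A woman who has already used Elitone has a reference for session length, strength and contraction, and 6.6 says that the sham differs on all three.

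If she recognises her arm, her diary may drift towards what she expects: fewer recorded leaks on active, more on sham. Both drifts widen the gap that the primary test measures, and the 2:1 allocation does not cancel them. Section 9.3 discounts unblinding of staff because staff do not report outcomes. That reassurance cannot extend to the subjects, who do.

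The trial supports an FDA request (6.7) with 60 planned completers, so a handful of such women could matter. As written, even a woman currently in another Elidah study could enrol.

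**Working it through.** **1. Is there a bar anywhere?** Read together, 4.1, 4.2, 4.3 and 11.2 contain no exclusion and no washout for Elitone exposure. Section 5.6 restricts new medications, not devices or other trials. Section 9.2 has no stratification by prior use.

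**2. Could such a woman tell the devices apart?** The documents compare as follows.

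| Feature | Active | Sham |
|---|---|---|
| Session | 20 minutes (6.2) | reduced, length not given (6.6) |
| Current | user-set, up to about 50 mA (6.4, 7.1) | lower (6.6) |
| Frequency | 2000 Hz base, modulated at 50 and 10 Hz (6.5) | higher (6.6) |
| Pelvic-floor contraction | intended | not intended (6.6) |

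Recognition is therefore plausible for a previous Elitone user, but it is an inference. For a user of another stimulator, such as the vaginal probes in 3.1, the sensation differs and the inference is weaker.

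**3. Check of the plan's test.** Section 9.5 uses a one-tailed Fisher exact test with p ≤ 0.025 on 40 against 20 women. For its example of 24/40 against 5/20 the test gives p = 0.0105, which agrees with the stated 0.01.

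**4. Illustration of size.** From the documents: 40 and 20 women, one-tailed Fisher at 0.025, and a 25% responder rate (the control rate in the 9.5 example). Assumed: no true device effect; a share f of women know their arm; their chance of being recorded as a responder moves by d, up on active and down on sham. Then

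- active rate = 0.25 + f·d
- sham rate = 0.25 − f·d

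For example, f = 0.20 and d = 0.20 give 0.25 + 0.04 = 0.29 and 0.25 − 0.04 = 0.21. The rejection probability is the sum of the binomial probabilities over all outcomes with Fisher p ≤ 0.025.

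| f (women of 60) | d = 10 points | d = 20 points |
|---|---|---|
| 0 | 1.3% | 1.3% |
| 10% (6) | 1.9% | 2.8% |
| 20% (12) | 2.8% | 5.6% |
| 30% (18) | 4.0% | 10.4% |

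With a 40% underlying rate, f = 20% gives 2.6% to 4.9%. The starting value is below 2.5% because Fisher's test is conservative at these sizes, and that slack absorbs a small share of unmasked women.

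**5. A harsher assumption.** If every unmasked woman reported at 60% on active and 10% on sham, whatever her true state, the 25% base would give 3.3%, 7.5% and 14.8% at f = 10%, 20% and 30%. At f = 5% it gives 2.1%.

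**The case against.** **Recognition is not shown.** The sham session length is not stated, intensity is set by the user, manuals were rewritten to remove cues, and the waveform was modified, so a past user might put a different feel down to a new version. This stands. It limits the claim to women who may recognise their arm. A reader might infer that the sham control fails for them; the documents do not show that.

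**The share may be tiny.** Advertising is nationwide without geographic targeting, and the sizes of the earlier studies are not given. This also stands. A reader might infer that 10% experienced users already break the 2.5% level. That holds under the large shifts in step 5, or with shifts of 20 points, but shifts of 10 to 15 points leave the rate at 1.9% to 2.3%.

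**Other harms are weak.** One might add that past responders would be over-represented, or that previous treatment spoils the baseline. But entry needs about one accident a day, checked against a 7-day untreated log that is the same in both arms (4.1, 5.4). Women whom the device cured would not qualify, and those who return could equally be past non-responders.

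**The study may not be ongoing.** Section 9.1 says that it is; 3.2 and 6.1 read as if it were finished. The gap exists either way, because past participants are not excluded.

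**Some protection exists.** The treatment guess is collected (6.6), and FORM-1 covers incontinence history. FORM-1 and FORM-13 are separate documents and may ask about earlier devices. Asking is not excluding, however, and no analysis uses the answers.

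**Conclusion.** The gap is real and worth closing before enrollment. Nothing in the eligibility sections keeps out current or former participants of the sponsor's Elitone studies, and the blinding argument in 9.3 does not address them, although they would record the primary outcome themselves.

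The size of the bias cannot be determined from the documents. Under assumed shifts of 10 to 20 points, a few such women do little harm. At about 20% (12 of 60), the false-positive rate exceeds the nominal 2.5% in each scenario tried, reaching 2.6% to 5.6% across the 25% and 40% base rates. These figures assume no true effect and that each woman in the share f actually knows her arm; they are not forecasts.

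The point is firm for Elitone exposure. It does not extend to a blanket exclusion of women who have used any pelvic-floor stimulator, for whom the documents give little reason to expect recognition.

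**What to change.** 1. Add to 4.2: current or prior participation in another Elidah/Elitone study, or prior use of the Elitone device. Ask this in the screening questions (FORM-13).
2. For other pelvic-floor stimulators, record prior use at screening, and add to 9.5 a sensitivity analysis of the primary endpoint without those women.
3. Reconcile the status of WIRB-20162650 between 9.1 and sections 3.2 and 6.1.

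The cost is one exclusion line, one or two screening questions and one extra analysis. A few candidates are lost. No sample-size figure changes. Matching candidates' names against the logs of the earlier studies before consent is not proposed, because the documents do not show that those logs could be used in this way.
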